6.1.7.3. Calculation of Relative Days

For both the start and the end dates of the concomitant medication records, their day relative to the day of first IP administration will be calculated as described in Section 4.3.1.

6.1.7.4. Presentation of Results

A frequency tabulation per planned treatment group and overall of the Anatomical Therapeutic Chemical (ATC) classification classes level 4 by therapeutic subgroup (ATC level 2) and generic term of the prior medication (defined as ‘prior only’ and ‘prior and concomitant’) will be provided as well as of the concomitant medication (defined as ‘concomitant only’ and ‘prior and concomitant’).

A listings of prior and concomitant medications will be provided. Also, prior and concomitant corticosteroid listing will be provided separately (the list of the ATC codes to be selected in this listing will be provided by the Galapagos medical services).

6.1.8. Procedures

Procedures results will only be listed.

6.1.9. Exposure to IP and Compliance

6.1.9.1. Derivation Rules

Derived Parameters: Extent of Exposure to IP

- *Total treatment duration (days)* = last IP administration date – first IP administration date + 1 day.

- *Total treatment duration, excluding days off IP*: Sum of the number of days with any IP administration.
- *Total treatment duration, full compliance* (days): Number of days where the complete volume of IP has been administered.

Derived Parameters: Compliance

- Overall compliance (%) = $100 \times \frac{\text{number of doses actually taken}}{\text{number of doses that should have been taken}}$
- Percent days with any intake (%) = $100 \times \frac{\text{total treatment duration,excluding days off drug}}{\text{total treatment duration}}$
- Percent days full compliance (%) = $100 \times \frac{\text{total treatment duration,fully compliant}}{\text{total treatment duration}}$

Derived Parameters: Extent of Exposure to MTX Drug

- *Total treatment duration* (days) = last MTX administration date – first MTX administration date + 1 day.
- *Total treatment duration, excluding days off MTX*: Sum of the number of days with any MTX administration.

6.1.9.2. Presentation of Results

Summary statistics per planned treatment group and overall will be provided for each compliance and extent of exposure parameter for IP administration. Frequency tables will be provided for the compliance parameters, using the following categories: <80%; 80% ≤ x < 100%; 100%; 100% < x ≤ 120%; > 120%.

All original IP administration records will be listed per subject. The listing will include all deviations from IP schedules such as missed or reduced doses and GLPG3970/placebo switches and will also include food intake status at the time of IP administration. IP exposure and compliance data will be listed.

For MTX administration, a table summarizing the number and percent of subjects taking MTX by planned treatment group and overall will be provided. In addition, the following parameters will be summarized:

- Dose at baseline (mg);
- Route at baseline;
- Dose form at baseline;
- *Total treatment duration* (days);
- *Total treatment duration, excluding days off MTX*

6.2. Efficacy Analyses

Efficacy analyses will be performed on the FAS.

Tabulations will be shown per planned treatment group.

6.2.1. Level of Significance

Statistical tests for efficacy analysis will be done at a 2-sided significance level of 10%.

6.2.2. Primary Efficacy Parameter

The primary endpoint for this study is the change from baseline in DAS28 (CRP) at Week 6. The DAS28 (CRP) is a derived measurement with differential weighting given to each component such as TJC28, SJC28, patient's global assessment of disease activity (0–100-mm VAS), and serum CRP level. A DAS28-CRP below the value of 2.6 is interpreted as Remission.

6.2.2.1. Derivation Rules

The DAS assessment is a derived measurement with differential weighting given to each component. The DAS28 (CRP) will be calculated at each assessment time point.

The components of the DAS28 arthritis assessment include:

- Tender Joint Count 28 (TJC28) ranges from 0-28
- Swollen Joint Count 28 (SJC28) ranges from 0-28
- High sensitivity C-reactive protein (hsCRP) (in mg/L)
- Patient's disease activity VAS (in mm) (ranges from 0 = best to 100 = worst)

The DAS28 (CRP) score will be calculated using the below formula:

$$\text{DAS28 (CRP)} = 0.56 \times \sqrt{\text{TJC28}} + 0.28 \times \sqrt{\text{SJC28}} + 0.36 \times \text{Ln}[1+\text{CRP}(\text{in mg/L})] + 0.014 \times \text{patient's disease activity VAS} (\text{in mm}) + 0.96 \text{ (Mack, Hsia, \& Aletaha, 2017)}$$

where Ln is the natural logarithm

A lower score is considered as better disease activity. If one of the component is missing at a specific analysis visit, DAS28 (CRP) will not be calculated for that assessment and will be set to missing.

6.2.2.2. Analyses Methods

DAS28 (CRP) data will be analyzed descriptively as actual (observed) values and changes from baseline. Percent change from baseline will not be calculated for the primary endpoint.

A MMRM will be used on the DAS28 (CRP) changes from baseline to compare treatment groups, with a 90% CI of the treatment difference at Week 6.

The following covariates will be used: treatment by visit interaction and baseline DAS28 by visit interaction. An unstructured variance-covariance matrix will be used to model the residuals. If the default Newton–Raphson algorithm used by SAS PROC MIXED fails to converge, the following will be tried to avoid lack of convergence while maintaining an unstructured variance:

- A. The Fisher scoring algorithm (via the SCORING=5 option of the PROC MIXED statement) will be used to obtain the initial values of covariance parameters.
- B. If the above fails, the no-diagonal factor analytic structure will be used which effectively performs the Cholesky decomposition via the TYPE=FA0(V) option of the REPEATED statement, where V is the total number of visits in the response vector (V = 3).
- C. If all the above fails, the variance-and-correlations parameterization will be attempted using TYPE =UNR

In the rare case where all the above fails, the Toeplitz structure with the sandwich variance estimator (EMPIRICAL option) will be used. If this option also fails, the AR(1) + random intercept model will be tried with the sandwich variance estimator.

The LSM, LSM difference between GLPG3970 and the placebo group (reference category), standard error, two-sided 90% CIs for the LSM and difference between treatment groups and p-value for treatment differences will be presented. The number of subjects in the analysis population and number of subjects in the analysis will be provided by treatment group.

Graphs of the mean (+- SE) actual values over time and of the mean (+- SE) change from baseline. In addition, profile line plots of the change from baseline will be provided by treatment group.

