2.2.3. Other Endpoints

2.3. Study Design

This is a Phase 2, randomized, double-blind, placebo-controlled, multicenter parallel-group study evaluating GLPG3970 in adult subjects with moderately to severely active RA and an inadequate response to MTX. In this study, subjects will receive 1 dose level of GLPG3970 (400 mg once daily [q.d.]) or placebo on top of their stable dose and dosing regimen of MTX.

The study is planned to randomize 25 subjects in a 3:2 ratio (15 subjects planned to receive GLPG3970 and 10 subjects planned to receive placebo).

The study will consist of 3 study periods:

[figure not shown]
- Screening period: up to 3 weeks with 1 study visit.
- Double-blind treatment period: 6 weeks with 4 study site visits (Days 1, 15, 29, and 43) and 1 telephone call (Day 8).
- Follow-up (FU) period: 2 weeks with 1 study visit.

Subjects will participate in the study for a maximum of 11 weeks (screening to FU) and will receive oral GLPG3970 or placebo, as a reconstituted oral solution, q.d. for 6 weeks.

Refer to the Schedule of Assessments (Section 2.5) for further details.

A schematic diagram of clinical study design, procedures and stages is provided in [Figure 1](#).

Figure 1 Schematic Diagram

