2.6. Sample Size Justification

The operating characteristics of the chosen decision framework at a sample size of 15 subjects (GLPG3970) + 10 subjects (placebo) are represented in the following graphical output and table, and were deemed acceptable. A common standard deviation (SD) of 1.3 for placebo and GLPG3970 was assumed based on previous experience with RA studies.

Lower Reference Value (LRV) and Target Value (TV) for the decision framework were determined based on the published studies and the therapies in development or on the market. They were identified by the project team as the lowest delta of possible interest and the best case scenario for efficacy outcome respectively.

A dropout rate of 20% was taken into account to allow a minimum of 20 subjects to complete the study. In case of drop-outs due to SARS-CoV-2 infection, additional subjects may be randomized on top of the planned sample size. The number of additional subjects randomized will not exceed the number of subjects dropping out of the study in relation to SARS-CoV-2. Randomization of additional subjects will ultimately be decided by the sponsor before any study lock or related unblinding has occurred.

Probability	Reference value	Outcome
0.852	-1.6	Signal detected
0.043	-1.6	No conclusion
0.105	-1.6	No signal detected
0.192	-0.6	Signal detected
0.091	-0.6	No conclusion
0.717	-0.6	No signal detected

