6.2.2.3. Decision Making Methodology

The decision making methodology described by Frewer et al (Frewer, Mitchell, Watkins, & Matcham, 2016) will be used to provide further insight into the treatment effect of GLPG3970 over placebo, and will support scenario analyses. The posterior distribution of this treatment effect will be estimated, and from this distribution probabilities of reaching at least a certain effect (delta) will be derived, e.g. a range of plausible effect size values going from as high as P ($\delta \leq -1.6$) to as low as P ($\delta \leq -0.6$).

The chosen framework parameters are as follows:

[figure not shown]
- TV: -1.6 and LRV: -0.6
- False stop risk: 10% and false go risk: 20%
- Framework rules:
 - o Signal detected if $P10 < TV$ and $P80 < LRV$
 - o No signal detected if $P10 \geq TV$
 - o No conclusion if $P10 < TV$

More details about this analysis will be provided in a separate document. This output will be generated for decision making purposes and will not be part of the CSR.

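### If the primary MMRM ever falls back to its last-resort models, the uncorrected sandwich estimator with 20 to 25 subjects will not hold the stated 10% level or 90% coverage

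*SAP*

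**What the plan says.** SAP 6.2.2.2 analyses change from baseline in DAS28 (CRP) by MMRM, "with a 90% CI of the treatment difference at Week 6". The mean model has treatment-by-visit and baseline-by-visit terms, three visits enter the response vector, and the residual covariance is unstructured. If the default algorithm fails, three steps are tried that still keep the matrix unstructured: Fisher scoring, a Cholesky-type factor-analytic form, and a variances-and-correlations form.

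Only if all three fail, which the SAP itself calls rare, does the covariance model change. Then "the Toeplitz structure with the sandwich variance estimator (EMPIRICAL option) will be used". If that also fails, "the AR(1) + random intercept model will be tried with the sandwich variance estimator". For neither model does the available text give a small-sample correction or a denominator degrees-of-freedom method. SAP 6.2.1 sets a two-sided 10% level, and 6.2.2.2 requires a standard error, a 90% CI and a p-value from whichever model is fitted.

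**The concern.** In PROC MIXED, the EMPIRICAL option is the classical sandwich. It uses raw residuals, which are smaller on average than the true errors because the model has been fitted to them. With many subjects the difference vanishes. With 15 and 10 subjects, or about 12 and 8 at Week 6, it does not.

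At stake is the purpose of a pre-specified fallback: the inference should be valid when the preferred model cannot be fitted. As written, the primary CI and p-value would lose their stated level in that situation, and a correction chosen afterwards would be post hoc.

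**Working it through.** **Inputs from the documents.** Allocation (SAP 2.3): "15 subjects planned to receive GLPG3970 and 10 subjects planned to receive placebo". SD (SAP 2.6): "A common standard deviation (SD) of 1.3 for placebo and GLPG3970 was assumed". Dropout (SAP 2.6): "A dropout rate of 20% was taken into account to allow a minimum of 20 subjects to complete the study". Level 10% two-sided (SAP 6.2.1). Three visits and the covariates as above (SAP 6.2.2.2).

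**Step 1. Reproduce the plan's own figure.** The documents give no error rate for the fallback, so the inputs are checked against the operating characteristics in SAP 2.6, using "TV: -1.6 and LRV: -0.6" and the P10/P80 rules of SAP 6.2.2.3.

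- SE = 1.3 × √(1/15 + 1/10) = 0.531.
- P10 < −1.6 requires an estimate below −1.6 + 1.2816 × 0.531 = −0.920.
- P80 < −0.6 requires an estimate below −0.6 − 0.8416 × 0.531 = −1.047.
- Signal / no conclusion / no signal at a true effect of −1.6: 0.851 / 0.049 / 0.100 (stated 0.852 / 0.043 / 0.105).
- At −0.6: 0.200 / 0.073 / 0.727 (stated 0.192 / 0.091 / 0.717).

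Every figure agrees within 2 points, so sample size and SD are read correctly.

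**Step 2. Direction and rough size by hand.** Ignore the baseline covariate. In an arm of size n, the expected squared residual is σ²(1 − 1/n). The expected classical sandwich variance of the difference is therefore σ²[(n₁−1)/n₁² + (n₀−1)/n₀²], against a true value of σ²(1/n₁ + 1/n₀).

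- 15+10: (14/225 + 9/100) / (1/15 + 1/10) = 0.1522/0.1667 = 0.913; square root 0.956.
- 12+8: (11/144 + 7/64) / (1/12 + 1/8) = 0.1858/0.2083 = 0.892; square root 0.944.

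The SE is thus about 4–6% too small before baseline is fitted. The covariate, and the variability of the estimated SE itself, add to this.

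**Step 3. Complete data, simulated under the null.** With the same covariates at every visit and no missing values, the Week 6 estimate equals a per-visit ANCOVA, and EMPIRICAL reduces to the HC0 sandwich. Between-subject df are subjects minus 3 (22 or 17). There were 200,000 runs per case, with equal SDs in the arms.

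| Rejection at nominal 10% | 15+10 | 12+8 |
|---|---|---|
| Classical sandwich, t on between-subject df | 12.7% | 13.5% |
| Classical sandwich, t on within-subject df | 13.5% | 14.5% |
| Classical sandwich, normal reference | 14.3% | 15.5% |
| Classical sandwich variance × n/(n−3), t | 10.6% | 10.8% |
| HC2-type (leverage) correction, t | 10.5% | 10.6% |
| HC3-type correction, t | 8.4% | 8.0% |
| Model-based SE, t | 10.1% | 10.1% |
| Mean sandwich SE / true SE | 0.919 | 0.895 |

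With the arm SDs in a ratio of 0.67 to 1.5, the classical sandwich ranged from 12.2% to 16.4% over all references.

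**Step 4. Full REML fits of both fallback models.** 15+10 subjects, three visits, random monotone dropout, about 4,000 runs per row (Monte Carlo SE about 0.5 points).

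| Model and setting | t, 22 df | t, 17 df | Within-subject df | Normal | SE ratio |
|---|---|---|---|---|---|
| Toeplitz, no dropout, correlation 0.6 | 12.5% | not applicable | 13.4% | 14.4% | 0.932 |
| Toeplitz, 20% dropout, correlation 0.6 | 14.0% | 13.4% | 14.5% | 15.4% | 0.892 |
| Toeplitz, 20% dropout, AR(1) 0.7 | 14.2% | 13.7% | 14.9% | 15.8% | 0.889 |
| Toeplitz, 20% dropout, SD 0.8/1.1/1.3 over visits | 14.1% | 13.5% | 14.8% | 15.9% | 0.886 |
| AR(1) + random intercept, 20% dropout, correlation 0.6 | 14.0% | 13.4% | 14.5% | 15.4% | 0.893 |

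SE ratios of 0.886–0.932 mean a shortfall of about 7–11%. Coverage is 100% minus the rejection rate: 100 − 12.5 = 87.5% down to 100 − 15.9 = 84.1%.

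**Step 5. How often would the branch be reached?** At three visits the unstructured matrix has 3 × 4/2 = 6 parameters. Unstructured REML was fitted to simulated 15+10 trials with correlations of 0.7/0.5. Failures were 0 of 1,000 (no dropout), 0 of 1,500 (20% dropout), 0 of 800 (40% dropout) and 0 of 1,000 (log-normal data, 20% dropout), so 0 of 4,300. A further 260 fits also gave none. Even if the branch were reached in 1% of trials, the overall error would rise by at most about 0.01 × (16% − 10%) = 0.06 points.

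**The case against.** The strongest reply is that this hardly ever matters. Three rescues come first, the SAP calls the remaining case rare, and Step 5 found no failure. That stands, with the limit that those fits used a numerical optimiser other than SAS. The study is also a 25-subject signal search at a 10% level.

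The exact excess depends on a reference distribution that the available text does not specify. The SAP's version history refers to SAS code in an appendix that is not in the text available for review, and a degrees-of-freedom method may be given there. This also stands. However, a t reference alone leaves 12.5–15%, so a df statement would not by itself cure the bias. The 15–16% figures mostly need a normal reference, which the SAP does not call for.

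Three stronger readings are tempting, and the documents do not support them:

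- A reader might infer that the primary analysis as planned has a 13–16% false-positive rate. It does not: the unstructured MMRM does not use the sandwich.
- A reader might infer that skewed joint counts or biomarkers make the fallback likely. Nothing shows this, and the skewed runs in Step 5 all converged. SAP 4.4.2 and 6.5.2 already put cytokines and metabolic markers on the log scale.
- A reader might infer that the signal decision of SAP 6.2.2.3 is distorted. Its details are left to a separate document, and nothing says that it would use the fallback standard error.

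**Conclusion.** The point holds for the fallback branch only, and it is minor. Both last-resort models use a variance estimator that is too small for this sample size, and no equal-variance or unequal-variance setting examined kept the 10% level. The error sizes assume normal errors, correlations mostly of 0.5–0.7 and random dropout. They were not conditioned on the unstructured model having failed first, which is the only situation in which they would apply. The absence of a correction is read from the available SAP text.

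**What to change.** In SAP 6.2.2.2, for both fallback models, replace the classical sandwich with a leverage-type (HC2-like) small-sample-corrected sandwich, for example through the EMPIRICAL= bias-correction options of PROC GLIMMIX. State a t reference on between-subject degrees of freedom: about 22 for 25 subjects (25 − 3) and about 17 for 20 (20 − 3). The HC2-type figure above is from complete data; the GLIMMIX options themselves were not simulated, so the programmer should confirm that the chosen option applies that correction. An HC3-type correction overshoots (8–9%).

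Simply deleting EMPIRICAL is not a safe alternative: model-based Toeplitz errors gave 16.7% (22 df, 20% dropout) when the SD grew over visits.

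The cost is one sentence and one code change, with slightly wider intervals only if the fallback is used. The sentence would also cover the other analyses that rest on this MMRM, such as the AUEC (6.2.2.4) and the between-group comparisons in 6.5.2.

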6.2.2.3. Decision Making Methodology

The decision making methodology described by Frewer et al (Frewer, Mitchell, Watkins, & Matcham, 2016) will be used to provide further insight into the treatment effect of GLPG3970 over placebo, and will support scenario analyses. The posterior distribution of this treatment effect will be estimated, and from this distribution probabilities of reaching at least a certain effect (delta) will be derived, e.g. a range of plausible effect size values going from as high as P ($\delta \leq -1.6$) to as low as P ($\delta \leq -0.6$).

The chosen framework parameters are as follows:

[figure not shown]
- TV: -1.6 and LRV: -0.6
- False stop risk: 10% and false go risk: 20%
- Framework rules:
 - o Signal detected if $P10 < TV$ and $P80 < LRV$
 - o No signal detected if $P10 \geq TV$
 - o No conclusion if $P10 < TV$

More details about this analysis will be provided in a separate document. This output will be generated for decision making purposes and will not be part of the CSR.

6.2.2.4. Area Under the Efficacy Curve (AUEC)

To further explore the data in a slightly different fashion, the area under the efficacy curve (AUEC) based on the MMRM-derived LS-means will be derived for GLPG3970 and placebo. The AUEC will be calculated using the trapezoidal rule as illustrated in Figure 2. A 90% confidence interval and between-group p-value will be derived as well. All will be based on the MMRM model for the DAS28(CRP) change from baseline.

Figure 2: Graphical illustration calculation AUEC

6.2.3. Secondary Efficacy Parameters

6.2.3.1. Disease Activity Score Based on 28 Joints (C-reactive Protein) [DAS28 (CRP)]: Binary/Ordinal Categorization

6.2.3.1.1 Derivation Rules

The binary categorizations of the DAS28 actual values calculated at each available time point are defined as follows:

- DAS28 remission: DAS28 < 2.6
- [REDACTED]

The ordinal categorization of the DAS28 actual values are defined as follows for each timepoint:

- High disease activity: > 5.1
- Moderate disease activity:] 3.2 , 5.1]
- Low disease activity: [2.6 , 3.2]
- Remission: < 2.6

If DAS28 values are missing at any time point, then corresponding binary and ordinal categories are also set to missing.

[REDACTED]

[REDACTED]

[figure not shown]
Actual DAS28(CRP)	Improvement (Reduction) in DAS28(CRP) from baseline:		
	> 1.2] 0.6, 1.2]	≤ 0.6
≤ 3.2	Good	Moderate	None
] 3.2, 5.1]	Moderate	Moderate	None
> 5.1	Moderate	None	None

6.2.3.1.2 Analysis Methods

The DAS28 remission will be summarized for the observed-case and non-responder imputation (NRI) using number and percentages by treatment group. Fisher's exact method will be used to compare the GLPG3970 and placebo based on NRI rates. Fisher's exact p-value and 90% CI of the difference between GLPG3970 and placebo will be presented.

Ordinal categorization of the DAS28 will be summarized using the descriptive table of the observed results with cumulative percentages by treatment group. A shift table from baseline to post-baseline visits will be provided.

A line plot over time and bar chart will be provided for the binary categorization of DAS28 (CRP) based on NRI cases.

6.2.3.2.2 Analysis Methods

Observed and change from baseline over time will be summarized using descriptive statistics by treatment group and visit.

A large black rectangular redaction box covers the majority of the page content, starting below the header and ending above the footer. The redaction is not perfectly uniform, with some irregular edges and small white gaps, suggesting it was created by a digital tool rather than a physical redactor.

A horizontal bar chart consisting of 20 bars arranged in two columns. The left column contains 10 bars, and the right column contains 10 bars. The bars are solid black with thin white outlines. The lengths of the bars decrease from left to right. The first bar in the left column is the longest, and the last bar in the right column is the shortest. The bars are set against a white background with no grid lines.

A large black rectangular redaction box covers the majority of the page content, from approximately y=113 to y=886. The redaction is not perfectly uniform, with some white space visible at the top and bottom edges. There are also a few small white rectangular areas within the black field, likely representing redacted images or specific text snippets.

The figure consists of a 10x10 grid of black bars on a white background. The bars are of varying lengths and are positioned in a staggered, non-overlapping manner. Some bars have small white segments at their ends, suggesting a stepped or layered structure. The bars are arranged in a way that creates a sense of depth and perspective, with some bars appearing to be in front of others. The overall effect is a minimalist and abstract representation of a grid or a set of data points.

